8.1.3 Psychometric, sleep and quality of life scales

Epworth sleepiness scale: scale commonly used in sleep medicine to evaluate daytime sleepiness in patients due to untreated (or undertreated) sleep apnea. As Modafinil has benefit in arousal, will track patients to see if they are reporting improved daytime sleepiness which could account for improved FOG if it occurred.

REM sleep behavior disorder (RBD) screening questionaire: parasomnias are commonly reported in PD and RBD is a prominent non-motor feature that is thought to be a pre-motor symptoms of the disease. As reticular activating pathways play a role in sleep, this will be used as measure to see if sleep is altered by Modafinil through its putative role in the reticular activating system.

Apathy evaluation scale (AES): Validated questionnaire to assess apathy in patients. Apathy has been reported as correlated with overall level of motor function and will be tracked to see if apathy improved with the treatment.

PDQ-39: validated questionnaire to assess overall quality of life in PD patients and will be tracked to determine whether any objective improvement in FOG overall leads to improved subjective assessment of quality of life.

PI: [name], PhD

Sponsor: UAMS

8.1.4 Other measures

Schwab and England Activities of Daily Living Scale: subjective global percentage assessment of overall function of PD patients that will be tracked over the trial.

Hoehn and Yahr scale staging of Parkinson's disease: staging scale, primarily developed for research based on unilateral, bilateral, postural stability and level of gait disability which will be tracked and requires no addition patient time, other than the UPDRS motor score above.

9.0 ADVERSE EVENTS

9.1 Experimental Therapy

While Modafinil does not have an indication in the treatment of freezing of gait in Parkinson disease it is FDA approved for the treatment of narcolepsy and has had a number of small clinical trials for use on various psychiatric conditions (ex. Depression and PTSD) but also is commonly used off label for daytime sleepiness. It has also been previously tested in Parkinson's disease patients with fatigue (total of 53 patients). ^{19, 20} For the most recent safety update, please refer to the commercially available drug insert for Modafinil (PROVIGIL).

Modafinil has previously been FDA approved for use in patients with narcolepsy. In clinical trials 151 protocol specified doses of up to 1600 mg/day have been administered to 32 subjects with no reported life-threatening events. Case reports of up to 4500 mg/dose also have not reported life-threatening events but reported excitation, agitation, insomnia and moderate elevation in hemodynamic parameters.

9.1.1 Contraindications:

- · Allergic reaction to any of the ingredients
- Have had a rash or allergic reaction to either Modafinil or armodafinil

PI: [name], PhD

Sponsor: UAMS

9.1.2 Special Warnings and Precautions for Use

Modafinil is a controlled substance as it can be abused and/or lead to dependence. Keep in a safe place to avoid misuse and abuse.

9.1.3 In-vitro data suggests that Modafinil is a weak inducer of CYP3A activity in a concentration dependent manner and therefore may reduce the effectiveness of drugs that are substrates for CYP3A enzymes (e.g. steroidal contraceptives, cyclosporine, midazolam, triazolam). Data also suggest that Modafinil is a weak inducer of CYP1A2, CYP2B6, and CYP2C9 (warfarin and phenytoin). Modafinil is also a reversible inhibitor of CYP2C19 and therefore may increase concentrations of drugs metabolized by this enzyme (e.g. phenytoin, diazepam, propranolol, omeprazole and clomipramine). Modafinil may interact with some CNS active drugs that PD patients may be using including certain tricyclic antidepressants (TCAs) (metabolized by CYP2C19) and selective serotonin uptake inhibitors (SSRIs) (metabolized by CYP2D6). Also concomitant administration of quetiapine reduced the systemic exposure of quetiapine. A recent report of a large overdose did not result in serious harmful effects.²¹

9.1.4 Adverse Events:

The following serious adverse reactions have been reported in the FDA approved label for Modafinil and will be monitored for including:

- serious rash (0.8%) including Stevens-Johnson Syndrome
- Angioedema and Anaphylaxis (one case reported out of 1595 patients)
- multi-organ hypersensitivity reactions
- persistent sleepiness
- psychiatric symptoms (0.3% including: mania, delusions, suicidal ideations, paranoid delusions, auditory hallucinations with doses of 600 mg/day)
- effect on ability to drive and use Machinery
- cardiovascular events (chest pain, palpitations, dyspnea, ischemic T-wave changes on electrocardiogram [occurred in 3 subjects with mitral valve prolapse or left ventricular hypertrophy], one episode of 9-seconds of asystole in a 35 year-old obese narcoleptic male with a prior history of syncope on 300 mg/day modafinil)

The following adverse reactions were reported in placebo controlled trials of Modafinil in Narcolepy, obstructive sleep apnea and shift work disorder in 1% or more of the modafinil treated group.

	modafinil (%) (n=934)	placebo (%) (n=567)
Headache	34	23
Nausea	11	3
Nervousness	7	3
Rhinitis	7	6
Back Pain	6	5
Diarrhea	6	5
Anxiety	5	1

Study Title: Modafinil for FOG (UAMS IRB#206341) PI: [name], PhD

Sponsor: UAMS

Dizziness	5	4
	5	4
Dyspepsia Insomnia	5	1
Anorexia		1
Dry Mouth	4	2
·	4	2
Pharyngitis Chest Pain	3	1
	3	1
Hypertension Abnormal Liver Function		
	2	1
Constipation		1
Depression	2	1
Palpitation	2	1
Paresthesia	2	0
Somnolence	2	1
Tachycardia	2	1
Vasodilatation	2	0
Abnormal Vision	1	0
Agitation	1	0
Asthma	1	0
Chills	1	0
Confusion	1	0
Dyskinesia	1	0
Edema	1	0
Emotional Lability	1	0
Eosinophilia	1	0
Epistaxis	1	0
Flatulence	1	0
Hyperkinesia	1	0
Hypertonia	1	0
Mouth Ulceration	1	0
Sweating	1	0
Taste Perversion	1	0
Thirst	1	0
Tremor	1	0
Urine Abnormality	1	0
Vertigo	1	0

Adverse Event Monitoring 9.2

Adverse event data collection and reporting, which are required as part of every clinical trial, are done to ensure the safety of Subjects enrolled in the studies as well as those

PI: [name], PhD

Sponsor: UAMS

who will enroll in future studies using similar agents. Adverse events are reported in a routine manner at scheduled times during a trial. Additionally, certain adverse events must be reported in an expedited manner to allow for optimal monitoring of subject safety and care.

9.3 Definitions

9.3.1 Definition of Adverse Event

An adverse event (AE) is any untoward medical occurrence in a subject receiving study treatment and which does not necessarily have a causal relationship with this treatment. An AE can therefore be any unfavorable and unintended sign (including an abnormal laboratory finding), symptom, or disease temporally associated with the use of an experimental intervention, whether or not related to the intervention.

9.3.2 Severity of Adverse Events

The severity of adverse events will be graded as follows:

Mild: the event causes discomfort without disruption of normal daily activities.

Moderate: the event causes discomfort that affects normal daily activities.

Severe: the event makes the patient unable to perform normal daily activities or significantly affects his/her clinical status.

9.3.3 Serious Adverse Events

A "serious" adverse event is defined in regulatory terminology as any untoward medical occurrence that meets one or more of the following criteria:

9.3.3.1 Results in death.

If death results from (progression of) the disease, the disease should be reported as event (SAE) itself.

9.3.3.2 Is life-threatening.

(the patient was at risk of death at the time of the event; it does not refer to an event that hypothetically might have caused death if it were more severe).

PI: [name], PhD

Sponsor: UAMS

9.3.3.3 Requires in-patient hospitalization or prolongation of existing hospitalization for ≥ 24 hours.

- **9.3.3.4** Results in persistent or significant disability or incapacity.
- **9.3.3.5** Is a congenital anomaly/birth defect
- 9.3.3.6 Is an important medical event
- 9.3.3.7 Any event that does not meet the above criteria, but that in the judgment of the investigator jeopardizes the patient, may be considered for reporting as a serious adverse event. The event may require medical or surgical intervention to prevent one of the outcomes listed in the definition of "Serious Adverse Event".

For example: allergic bronchospasm requiring intensive treatment in an emergency room or at home; convulsions that may not result in hospitalization; development of drug abuse or drug dependency.

9.4 Steps to Determine If an Adverse Event Requires Expedited Reporting

Step 1: Identify the adverse event.

Step 2: Determine whether the adverse event is related to the protocol therapy. Attribution categories are as follows:

- Definite The AE is clearly related to the study treatment.
- Probable The AE is likely related to the study treatment.
- Possible The AE *may be related* to the study treatment.
- Unrelated The AE is clearly NOT related to the study treatment.

Step 3: Determine the prior experience of the adverse event.

Expected events are those that have been previously identified as resulting from administration of the agent. An adverse event is considered unexpected, for expedited reporting purposes only, when either the type of event or the severity of the event is not listed in:

- the current known adverse events listed in the Agent Information Section of this protocol;
- the drug package insert;

Step 4: Determine whether the adverse event is a Serious Adverse Event

9.5 Reporting Requirements for Adverse Events

9.5.1 Expedited Reporting

- The Principal Investigator must be notified within 24 hours of learning of any serious adverse events, regardless of attribution, occurring during the study.
- The IRB must be notified within 10 business days of any unanticipated problems involving risk to subjects or others" (UPIRTSO). A UPIRTSO is defined as any problem, event or new information that is:
 - 1. Unanticipated or unexpected;
 - 2. Related to the research; and
 - 3. Involves new or increased risks to subjects or others.

PI: [name], PhD

Sponsor: UAMS

 The FDA should be notified within 7 business days of the PI learning of any unexpected fatal or life-threatening adverse event with possible relationship to study drug, and 15 business days of the Sponsor learning of any event that is considered: 1) serious, 2) unexpected, and 3) at least possibly related to study participation.

9.5.2 Routine Reporting

 All other adverse events- such as those that are expected, or are unlikely or definitely not related to the study participation- are to be reported annually as part of regular data submission.

9.6 Unblinding Procedures

Depending upon the AE or if there is a SAE or unforeseen event, the treatment of the subject may need to be unblinded as part of management of the event at the discretion of the PI. The IRB will be notified within 10 days of the unblinding and it will be documented in the subject's source document.

9.7 Stopping Rules

Dosing of a particular subject may be stopped prematurely by the principle investigator if the subject:

- 1. Experiences an intolerable adverse event (see section 6.3);
- 2. Develops a clinically significant laboratory or ECG abnormality;
- 3. Develops an allergic or anaphylactoid reaction to the medication;
- 4. The principal investigator consider that the number and/or severity of adverse events justify discontinuation of the study

10.0 STATISTICAL CONSIDERATIONS

The study is a prospective repeated measures longitudinal design. The primary outcome response is the FOG-Q total score and the stride length changes, and the secondary responses are the UPDRS Part III subscale, the PDQ-39, the RBD scale, and the Epworth Sleepiness Scale. These measures will be observed at 6 time points for both study arms. A primary statistical goal is to estimate the mean response at all six time points for each group and subsequently estimate changes in the outcome measures for each study group from baseline. Additionally, it is of interest to estimate the how the study groups differ in their mean change from baseline. A two group repeated measures linear model will be employed to determine significance for within each group and then to compare among the groups. Significance will be declared at the 5% level of significance and Bonferroni methods will be used for multiple comparisons. This analysis approach will be applied to the primary and secondary responses.

The study calls for 10 subjects in both arms for a total of 20 patients. Within a study arm the linear model will have in excess of 80% power to detect a 1.75 unit difference in observed means. Based on standard deviation estimates from previous researchers in similar settings,²² the FOGQ (the primary response) has a standard deviation of 3.58. This implies that we will have power to detect a 6.265 (1.75*3.58) unit difference among time point means at the 5% level of significance. Power calculations are from 'Tables of Sample Sizes in the Analysis of Variance' published by Bratcher.²³

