4.4 Endpoints

4.4.1 Primary Endpoints

- 4.4.1.1 To determine if 50 mg/day Modafinil decreases freezing of gait in PD patients with FOG compared with placebo as measured by the Giladi Freezing of gait questionnaire (FOG-Q) after 12 weeks of active treatment or placebo. Subjects who drop out of the study after at least 6 weeks of either treatment arm will be included in this analysis.
- 4.4.1.2 To determine if 50 mg/day Modafinil decreased the decline stride length seen in PD patients with FOG. The rate of decline in stride length will be compared plotting the stride length at steady state in subjects in the early and late-start arms to determine if the rate of decline improves in subjects taking Modafinil in the early-start arm and whether this rate of decline also improves in the second phase of the trial in the delayed-start arm.

We will also determine if at the completion of 24 weeks, the early-start arm has differential change in slope of other continuous gait parameters (stride width, gait cycle time, gait cycle velocity, swing and stance percent, total single and double support time, cadence) compared to the delayed start arm suggesting that Modafinil slows the progression of the gait decline.

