4.4.2 Secondary Endpoints

- 4.4.2.1 To determine if 50 mg/day Modafinil improves motor function in PD patients with FOG compared to placebo as measured by the UPDRS Part III motor subscale after 12 weeks of active treatment or placebo. Subjects who drop out of the study after at least 6 weeks of either treatment arm will be included in this analysis.
- 4.4.2.2 To describe the adverse events associated with Modafinil dosed at 50 mg/day in patients treated for 3 months (delayed start arm) and 6 months (early start arm) in Parkinson's disease patients.
- 4.4.2.3 To determine if quality of life is improved with Modafinil as measured by the PDQ-39 after 12 weeks of active treatment or placebo. Subjects who drop out of the study after at least 6 weeks of either treatment arm will be included in this analysis.
- **4.4.2.4** To determine if sleep disorders are improved with Modafinil as measured by the RBD scale and Epworth Sleepiness Scale after 12 weeks of active treatment or placebo. Subjects who drop out of the

PI: [name], PhD

Sponsor: UAMS

study after at least 6 weeks of either treatment arm will be included in this analysis.

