- 15. Frontal assessment battery (FAB) every 12 weeks and at visit six (5-10 minutes).

16

Study Title: Modafinil for FOG (UAMS IRB#206341) PI: [name], PhD

Sponsor: UAMS

- 16. Stroop test every 12 weeks and at visit six (3-5 minutes).
- 17. Scales for outcome in Parkinson's disease cognition (SCOPA-COG) every 12 weeks and at visit six (10-15 minutes).

7.3 **Schedule of Time and Events Table**

Activity	Visit 1 (Screening Visit)	Visit 2 (6 weeks)	Visit 3 (12 weeks)	Visit 4 (18 weeks)	Visit 5 (24 weeks)	Visit 6 (26 weeks)
Inclusion/Exclusion	Х					
Informed Consent Signed	Х					
HIPAA Authorization Signed	Х					
Demographic Information	Х					
Vital Signs ¹	Х	Х	Х	Х	Х	Х
Medication Profile ¹	Х	Х	Х	Х	Х	Х
Complete Neurological Examination ¹	Х		Х		Х	Х
Complete Movement Disorders Examination ¹	Х	Х	Х	Х	Х	Х
Gait and Balance Measurements ¹	Х	Х	Х	Х	Х	Х
Unified Parkinson's Disease Rating Scale (UPDRS) ¹	х	Х	х	х	х	х
Freezing of Gait Questionnaire (FOG-Q or NFOG-Q) ¹	х	Х	х	х	х	х
Schwab & England Activities of Daily Living Scale ¹	х	Х	х	х	х	Х
Hoehn & Yahr Scale Staging of Parkinson's Disease ¹	х	Х	х	х	х	Х
Montreal Cognitive Assessment (MoCA) ¹	Х		Х		Х	Х
Frontal Assessment Battery (FAB) ¹	Х		Х		Х	Х
Stroop Test ¹	Х		Х		Х	Х
Scales for Outcome in Parkinson's Disease – Cognition (SCOPA-COG)	х		х		х	х

PI: [name], PhD

Sponsor: UAMS

Epworth Sleepiness Scale ²	х	х	Х	Х	х	х
REM Sleep Behavior Disorder Screening Questionnaire ²	×	Х	x	x	×	х
Apathy Evaluation Scale (AES-S) ²	Х	х	Х	Х	Х	Х
Parkinson's Disease Questionnaire for Quality of Life (PDQ-39) ²	х	Х	х	х	х	х

¹ Study staff performed

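### Adjusting the week-12 FOG-Q comparison for the Visit 1 score would usually be more precise than Section 10's mean-change contrast, by an amount that depends on a correlation the documents do not give

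*Combined protocol and SAP*

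**What the plan says.** Section 10 treats baseline as one of six response times and sets out to estimate each arm's mean at every one. On the comparison between arms it adds that "it is of interest to estimate the how the study groups differ in their mean change from baseline". The model is given in one sentence: "A two group repeated measures linear model will be employed to determine significance for within each group and then to compare among the groups". No covariate and no common baseline mean is named there or elsewhere in the document.

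The visit for the FOG-Q comparison comes from 4.4.1.1: "FOG-Q) after 12 weeks of active treatment or placebo". The same item keeps early leavers: "Subjects who drop out of the study after at least 6 weeks of either treatment arm will be included in this analysis". Section 4.4.2 uses the same time frame for the secondary scales, for example "as measured by the PDQ-39 after 12 weeks of active treatment or placebo". The schedule in 7.3 marks the FOG-Q at Visit 1 and at every later visit.

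Stride length is handled differently. Item 4.4.1.2 defines it through rates of decline, including "whether this rate of decline also improves in the second phase of the trial in the delayed-start arm", so this point does not reach it or the other gait slopes.

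**The concern.** Arms of 10 will differ at baseline by chance. A change score subtracts the whole of that difference from the week-12 result, although only part of it carries forward to week 12 unless the two scores are highly correlated. An adjusted analysis estimates how much carries over and removes only that part, from the same data. What is at stake is the precision of the primary comparison with placebo in a trial of 20 patients. The validity of the comparison is not at stake.

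**Working it through.** **Inputs from the document.** 10 per arm; 5% level; "the FOGQ (the primary response) has a standard deviation of 3.58" (all Section 10); entry requires FOG-Q above 8 (5.1); a 10% change is sought on a 24-point scale (8.1.1), taken here as 2.4 points.

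**Assumed, because the document is silent.** Two-sided test; 10 evaluable per arm; baseline to week-12 correlation ρ of 0.3 to 0.8; equal SDs at both visits unless stated.

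**The plan's own figure.** 1.75 × 3.58 = 6.265. A one-way analysis of variance with six time points, 10 per point and noncentrality 10 × 1.75²/2 = 15.3 gives 83.4% power on 5 and 54 df, so the claim of more than 80% reproduces. It is a within-arm figure; Section 10 gives no between-arm power.

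**What the planned contrast is.** A group-by-visit mixed model with baseline as a response and free group means was fitted to one simulated complete data set. Its week-12 contrast equalled the raw difference in mean change (2.4245 both ways).

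**Chance imbalance.** The SD of the baseline difference between arms is 3.58 × √(2/10) = 1.60 points.

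**Equal SDs, no pooling of error across visits.**
- Change score: variance 3.58² × 2(1 − ρ), 18 df.
- Adjusted: variance 3.58² × (1 − ρ²) × 17/16, 17 df. The 1/16 = 1/(20 − 4) is the expected cost of estimating the slope.
- Standard error = √(variance × 2/10). Detectable differences are at 80% power from the noncentral t distribution.

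| ρ | SE, change | SE, adjusted | Detectable, change | Detectable, adjusted | Variance saving |
|---|---|---|---|---|---|
| 0.3 | 1.89 | 1.57 | 5.61 | 4.68 | 31% |
| 0.5 | 1.60 | 1.43 | 4.74 | 4.25 | 20% |
| 0.7 | 1.24 | 1.18 | 3.67 | 3.50 | 10% |
| 0.8 | 1.01 | 0.99 | 3.00 | 2.94 | 4% |

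Simulation (40,000 trials per ρ) gave adjusted/change variance ratios of 0.69, 0.80 and 0.90 at ρ = 0.3, 0.5 and 0.7. The detectable differences cross at ρ of about 0.87.

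**Error pooled across visits (compound symmetry, covariate version).** Detectable differences go from 5.36 to 4.39, 4.53 to 4.01, 3.51 to 3.32 and 2.87 to 2.79. The savings are 33%, 23%, 12% and 7%, with break-even near 0.89. Error df fall from 90 to about 48 to 72.

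**Unequal SDs, correlation unchanged, no pooling.** Let k be baseline SD divided by week-12 SD. In units of 3.58², the change-score variance is 1 + k² − 2ρk = (1 − ρ²) + (k − ρ)². Adjustment loses when (k − ρ)² < (1 − ρ²)/16, that is, for k within ρ ± 0.25√(1 − ρ²).
- ρ = 0.5: upper limit 0.5 + 0.217 = about 0.72. Savings at k = 0.9, 0.8, 0.7 are 12%, 5%, −1%.
- ρ = 0.7: upper limit 0.7 + 0.179 = about 0.88. Savings are 1%, −4%, −6%.
- ρ = 0.8: limits 0.8 ± 0.15 = 0.65 and 0.95. Savings are −3%, −6%, −3%.

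Because (k − ρ)² cannot be negative, the loss cannot exceed 1/16, about 6% of variance.

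**Baseline narrowed by selection, slope b unchanged, no pooling.** The change-score variance is 3.58² × [(1 − b²) + (1 − b)²k²], with k now the baseline SD relative to its unselected value. Savings at k = 0.9, 0.8, 0.7:
- b = 0.5: 16%, 12%, 9%.
- b = 0.7: 7%, 5%, 2%.
- b = 0.8: about 2.5%, 1%, −1%.

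**Power for 2.4 points (equal SDs, no pooling).** 29% to 35% at ρ = 0.5; 45% to 48% at ρ = 0.7.

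**The case against.** The strongest reply is that the deciding quantity is absent. The document gives no baseline to week-12 correlation and no baseline SD for these patients. Stable therapy is required at entry (5.1) and patients likely to need medication changes are excluded (5.2), which makes a high correlation plausible. At 0.7 to 0.8 with equal SDs, the detectable difference improves by only 0.17 to 0.06 points. The entry threshold may also narrow the baseline SD, and at an unchanged correlation even modest narrowing cancels or reverses a gain of that size. All of this stands and limits the size of the claim. It does not remove the claim, because the possible loss is bounded at about 6% of variance while the possible saving at equal SDs reaches about 30%.

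It is also fair to say that the absence of adjustment is inferred. Section 10 does not use the word unadjusted and does not rule out a covariate or a common baseline mean. Separate means for each arm at six visits favour the unadjusted reading, but a sentence from the sponsor could settle it the other way.

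Finally, this is a pilot, and Section 10 presents the between-arm contrast as an additional interest. That is a reason to treat the point as optional. Even so, 4.1.1 and 4.4.1.1 make the comparison with placebo a primary objective.

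A reader might go further and infer that the mean-change analysis is biased. The document does not support that: allocation is randomised 1:1, and the contrast is unbiased under randomisation.

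**Conclusion.** The point holds as an optional precision improvement, not as an error. Under equal SDs of 3.58, 10 evaluable patients per arm, a two-sided 5% test and no pooling, baseline adjustment saves from 31% of the variance at correlation 0.3 down to 4% at 0.8, and nothing from about 0.87. With a narrower baseline at an unchanged correlation, the saving disappears below an SD ratio of about 0.72 at correlation 0.5, below about 0.88 at 0.7, and between about 0.65 and 0.95 at 0.8. Unequal SDs were not examined with pooling. The figures are for the covariate version; the common-baseline version was not computed separately.

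A reader might infer that adjustment would make the trial adequately powered, or that it always helps. Neither follows: power for 2.4 points stays low at correlation 0.5, and the direction can reverse in the cases shown.

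**What to change.** In Section 10, state that the week-12 between-arm FOG-Q difference set by 4.4.1.1 is estimated from the six-visit repeated-measures model with visit-by-arm terms and one common baseline mean for the two randomised arms. This keeps Visit 1 as a response, so means at all six visits are still produced. If the planned model already has this constraint, it is enough to say so. A Visit 1 covariate is an alternative; the covariate version drops Visit 1 as a response, so the within-arm tests would then be run in the model as planned.

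State also that patients who leave after at least 6 weeks enter through their observed visits. The same may be done for the week-12 secondary scales, but no gain can be quantified because the document gives no SDs for them. The alpha level, stride length and the other gait slope analyses stay as planned.

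The cost is SAP wording and no new data. Without pooling it uses one degree of freedom. With pooling, the covariate version has fewer error degrees of freedom, about 48 to 72 against 90.

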6.2 Treatment Dosage and Administration

The research pharmacy will create a randomization log, randomizing 20 subjects 1:1 to early start or delayed start modafinil (Figure 1). Subjects will be assigned the next line in the log in order of treatment. Subjects in the early-start arm will receive Modafinil 50 mg oral daily (a.m.) for 24 weeks while subjects in the delayed-start arm will receive oral placebo for the first 12 weeks of active treatment followed by Modafinil 50 mg oral daily for weeks 13-24 of the active treatment period. The drug will be washed out for a 2 week period with repeat assessments to determine any withdrawal symptoms.

[figure not shown]

Figure 1: Delayed-start trial model with 1:1 randomization into an early-start arm with 10 subjects receiving Modafinil 50 mg oral daily for 24 weeks and 10 subjects randomized to a delayed-start arm receiving placebo for the 1st 12 weeks followed by Modafinil 50mg oral daily for weeks 13-24. Visits will be performed at initiation and randomization, followed by 6, 12, 18 and 24 week visits in the active phase with the final visit performed after a 2 week drug washout phase.

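### Section 10 does not name the week-12 between-arm FOG-Q contrast as the primary test and leaves the Bonferroni family undefined, so the test may be divided by comparisons that its claim does not need

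*Combined protocol and SAP*

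**What the plan says.** Section 4.4.1.1 sets the FOG-Q primary endpoint as a comparison of modafinil with placebo, "as measured by the Giladi Freezing of gait questionnaire (FOG-Q) after 12 weeks of active treatment or placebo". That is one visit and one between-arm contrast.

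Section 10 takes a wider view. On the visits it says: "These measures will be observed at 6 time points for both study arms". It makes estimation of the six visit means in each arm, and of changes from baseline, a primary statistical goal, and adds the between-arm difference in mean change as a further interest. One repeated-measures model is to test within each arm first and then compare the arms. The multiplicity rule is one sentence: "Significance will be declared at the 5% level of significance and Bonferroni methods will be used for multiple comparisons". Section 10 does not mention week 12, list the comparisons in the family, count them, or say whether the contrast in 4.4.1.1 is among them.

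The placebo period is short. Section 6.2 (Figure 1 legend) describes the delayed-start arm as "receiving placebo for the 1st 12 weeks followed by Modafinil 50mg oral daily for weeks 13-24". Section 4.0 adds a 2-week washout with an assessment at week 26.

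The only power statement is for time points within one arm: "Within a study arm the linear model will have in excess of 80% power to detect a 1.75 unit difference in observed means".

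**The concern.** A prespecified single contrast needs no correction for other visits, because its visit was fixed in advance. Section 10 does not protect it in this way. The Bonferroni sentence directly follows the description of within-arm and between-arm comparisons over six visits, so the natural reading is that it covers them.

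Of the five post-baseline between-arm contrasts, only weeks 6 and 12 have a concurrent placebo arm. Weeks 18 and 24 compare modafinil with modafinil, and week 26 compares two arms off drug. The within-arm changes are not randomised comparisons. Dividing the week-12 alpha among these adds no protection that the week-12 claim requires.

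Two things are at stake. With 10 per arm, the primary placebo comparison could lose power for nothing. And with the family undefined, the number of tests could be settled after the data are seen.

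**Working it through.** **Inputs.** From Section 10: 5% level; 10 per arm ("The study calls for 10 subjects in both arms for a total of 20 patients"); six visits, hence five post-baseline changes; effect 1.75 SD; and "the FOGQ (the primary response) has a standard deviation of 3.58". Assumed here: two-sided tests and 10 completers per arm. The family size m is varied because the plan does not give it.

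**1. The plan's own figure.** 1.75 × 3.58 = 6.265 points, as stated: "This implies that we will have power to detect a 6.265 (1.75*3.58) unit difference among time point means at the 5% level of significance". Treat this as an F-test of six means with n = 10 in the least favourable configuration. The noncentrality is n × 1.75² / 2 = 10 × 3.0625 / 2 = 15.3. With 5 and 54 df at 5%, power is 83.4%; with 5 and 45 df (repeated measures, zero correlation) it is 82.5%. The claim of more than 80% reproduces, but as a within-arm figure. It is not the power of the week-12 placebo contrast.

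**2. Formula for the between-arm contrast.** A two-sample t-test on 18 df at level 0.05/m, with noncentrality d × √(n/2) = d × √5, where d is the effect divided by the SD of the contrast variable. Power is the probability that the noncentral t exceeds the critical value.

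**3. Benchmark effect.** The value of d giving 80% power at m = 1 is 1.325 (noncentrality 2.963). This is a benchmark, not a figure from the plan. The right-hand column uses the plan's 1.75 SD between arms (noncentrality 3.913), taking the SD of the contrast as 3.58.

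| m | level | critical t | power, d = 1.325 | power, d = 1.75 |
|---|---|---|---|---|
| 1 | 0.05 | 2.101 | 80.0% | 95.9% |
| 2 | 0.025 | 2.445 | 69.6% | 91.8% |
| 4 | 0.0125 | 2.775 | 58.2% | 85.8% |
| 5 | 0.01 | 2.878 | 54.5% | 83.4% |
| 15 | 0.00333 | 3.380 | 37.4% | 69.4% |

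Here m = 2 is weeks 6 and 12; m = 4 is week 12 with weeks 18, 24 and 26; m = 5 is all post-baseline between-arm contrasts; and m = 15 adds the five changes from baseline in each arm (5 + 2 × 5).

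**4. Share due to visits without placebo.** At m = 5 the benchmark loses 80.0 − 54.5 = 25.5 points. Dropping weeks 18, 24 and 26 leaves m = 2, so those visits account for 69.6 − 54.5 = 15.1 points. The other 10.4 come from week 6, which is placebo-controlled but is not the primary visit.

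**5. Sensitivity to the SD.** If the test is on change from baseline, its SD is 3.58 × √(2(1 − ρ)), where ρ is the within-subject correlation, which the plan does not give. For a 6.265-point effect:

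| ρ (assumed) | SD of change | m = 1 | m = 5 |
|---|---|---|---|
| 0 | 5.06 | 74.4% | 47.5% |
| 0.3 | 4.24 | 87.8% | 66.5% |
| 0.5 | 3.58 | 95.9% | 83.4% |
| 0.7 | 2.77 | 99.8% | 97.7% |

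**6. A smaller effect.** Section 8.1.1 looks for a 10% FOG-Q change, which is 2.4 points if taken on the 24-point scale. With SD 3.58, d = 2.4 / 3.58 = 0.67, and power is 29.4% at m = 1 and 11.3% at m = 5.

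**The case against.** The strongest reply is that the penalty is inferred. The Bonferroni sentence names no family. A narrower reading, in which it covers only pairwise follow-up tests in the repeated-measures model and 4.4.1.1 stands alone, is possible. This stands: the loss is conditional on how the family is read. It does not answer the point, because the plan gives no way to choose between the readings.

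A reader might infer that the plan cuts the power of its primary test from 80% to 54% or less. The documents do not support that. The 80% in Section 10 is within-arm, no between-arm power is stated, and 54% belongs to one assumed effect and five tests. Smaller families or larger effects give more.

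A reader might also blame the whole loss on weeks 18, 24 and 26. They explain about 15 of the 25.5 points at five tests; week 6 explains the rest.

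It can further be said that this is a pilot with estimation as a stated goal, and that later visits matter in a delayed-start design. Both are fair. The first limits how serious the point is. The second limits the remedy: Section 4.4.1.2 asks about stride-length decline in the delayed arm's second phase and about other gait slopes at 24 weeks, and Section 4.4.3.1 asks about extra early-start benefit on cognition at 24 weeks. A general ban on tests after week 12 would remove questions the protocol poses.

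**Conclusion.** The point holds in conditional form. Section 10 does not identify the week-12 between-arm FOG-Q contrast as the primary test, does not define the Bonferroni family, and states no between-arm power. If the family spans the visits, a benchmark effect with 80% power unadjusted falls to about 70%, 54% or 37% for 2, 5 or 15 tests. The plan's 1.75 SD, applied between arms, falls from 96% to 83% or 69% for 5 or 15 tests. These figures rest on two-sided tests, 10 completers per arm and 18 df; the 1.75 SD figures also assume a contrast SD of 3.58. The actual loss cannot be stated until the family is defined. This should be corrected because it is cheap, but it does not invalidate the design.

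**What to change.** In Section 10:

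- State that the FOG-Q primary test is the single week-12 difference between arms in change from baseline, estimated from the repeated-measures model. Test it at the alpha allocated to FOG-Q, keeping any split with stride length, with no division for other visits or within-arm tests.
- For FOG-Q only, report the other visits and all within-arm changes as estimates with 95% intervals.
- Keep the stride-length and gait-slope questions (4.4.1.2) and the 24-week cognitive question (4.4.3.1) as separate analyses.
- Where a family of tests remains, list its members and use Holm in place of plain Bonferroni. Holm controls the same error rate and is never less powerful.
- State the between-arm power for the week-12 contrast, with the SD and correlation assumed.

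The cost is wording only; visits, treatment and sample size do not change. The downside is that no significance claim could be made for FOG-Q at visits other than week 12 or for changes within an arm.
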